9.8. Quality Control

This is a retrospective study, so issues of quality control at study sites, eg, data clarification queries, do not apply. Analyses are programmed according the specifications in the protocol's SAP and all code and other technical artifacts are documented and stored following established programming practices on Pfizer servers and in Pfizer's Global Document Management System. Quality control (QC) will follow the Flatiron's standard procedure for quality control and assurance as described in Flatiron Health Analytic Database Parent Protocol. QC for structured and unstructured data is conducted prior to delivery of each dataset. For each data model, Flatiron generates and continually maintains a set of quality standards and versioned business rules. These QC standards cover themes such as demographics, biomarkers, treatment, therapy shares, treatment length/dosage, lines of therapy, real world recurrence, and real world progression free survival. They have a team of 900 expert nurse and physician abstractors that co-create and version rules, and also to create QC that includes both medical considerations (eg, what are expected based on the literature and clinical practice) and data considerations (eg, stability from prior months). Missingness of death data is a major confounding factor for many real-world oncology analyses. For survival data, Flatiron Health utilizes four resources, including the National Death Index, US Social Security Death Index, obituaries and commercial death data published from a vendor to identify when patients have died

(<https://onlinelibrary.wiley.com/doi/full/10.1111/1475-6773.12872>). In a study of advanced non-small cell lung cancer patients, sensitivity increased from 66% from Flatiron's HER-based registry alone to over 91% from the composite of the four sources.

QC will be performed for the results of the study, including reviewing and double checking for correct data, consistency, spelling, grammar and structure. It is also reviewed to ensure that it conforms to Flatiron's data dictionary, has internal consistency (eg, that date of diagnosis occurs after date of birth) and meets the study objectives. The final review of the findings and content will be conducted in a summary presentation.

9.9. Limitations of the Research Methods

The proposed study may have the following limitations.

One of the main challenges of EHR data is the potential for missing, inaccurate or incomplete data. For example, EHR contains only that a physician prescribed a drug but not whether it was filled/refilled. The quality of information extracted from the EHR depends on the quality of information entered the EHR by the clinician. Feeds of EHR data may be updated only every 3-6 months, with some vendors providing more rapid updates. Data quality, missingness and other challenges are mitigated with Flatiron's semi-automated enhanced curation and quality control, though these challenges are not fully obviated by these expert biocurators, rules and processes.

The patient populations in the Flatiron database may not be reflective of the general population nationally. Some skewing in the data is possible if differences exist between patients in this study cohort and general patient population. Thus, the results of this study will be unprojected (ie, analyses will be based on the sample collected and not projected to the national level).

Due to the nature of the data employed in this study, it is not feasible to make an assessment of causality between medical events recorded and the medicinal products at an individual case level. As a result of the way this study is designed, no causal inference can be ascertained, as this is an observational study using retrospective data. Secondary data does not report the causality.

In addition, sample size may limit subgroup analyses and generalizability of the findings.

9.10. Other Aspects

Not applicable.

10. PROTECTION OF HUMAN SUBJECTS

10.1. Patient Information

All parties will comply with all applicable laws, including laws regarding the implementation of organizational and technical measures to ensure protection of patient personal data. Such measures will include omitting patient names or other directly identifiable data in any reports, publications, or other disclosures, except where required by applicable laws.

Patient personal data will be stored at Flatiron in *encrypted electronic* form and will be *password protected* to ensure that only authorized study staff has access. Flatiron will implement appropriate technical and organizational measures to ensure that the personal data can be recovered in the event of disaster. In the event of a potential personal data breach, Flatiron shall be responsible for determining whether a personal data breach has in fact occurred and, if so, providing breach notifications as required by law.

To protect the rights and freedoms of natural persons with regard to the processing of personal data, when study data are compiled for transfer to Pfizer and other authorized parties, any patient names will be removed and will be replaced by a single, specific, numerical code. All other identifiable data transferred to Pfizer or other authorized parties will be identified by this single, patient-specific code. In case of data transfer, Pfizer will maintain high standards of confidentiality and protection of patients' personal data consistent with the *statement of work with Flatiron* and applicable privacy laws.

10.2. Patient Consent

As this study involves de-identified data, which according to applicable legal requirements do not contain data subject to privacy laws, obtaining informed consent from patients by Pfizer is not required.

10.3. Patient Withdrawal

Not applicable.

10.4. Institutional Review Board (IRB)/Independent Ethics Committee (IEC)

The IRB approval of this observational study with secondary data use from an existing EHR database is covered by IRB approval on Flatiron parent protocol. Data provided by Flatiron to third parties were de-identified and provisions were in place to prevent re-identification in order to protect patients' confidentiality. This study is exempt from institutional review board approval because it is retrospective, non-interventional, and will use anonymized data provided by Flatiron.

10.5. Ethical Conduct of the Study

The study will be conducted in accordance with legal and regulatory requirements, as well as with scientific purpose, value and rigor and follow generally accepted Guidelines for Good Pharmacoepidemiology Practices (GPP) issued by the International Society for Pharmacoepidemiology (ISPE) research practices (https://www.pharmacoepi.org/resources/guidelines_08027.cfm), Good Practices for Outcomes Research issued by the International Society for Pharmacoeconomics and Outcomes Research (ISPOR) (http://www.ispor.org/workpaper/practices_index.asp) and Good practices for real-world data studies of treatment and/or comparative effectiveness: Recommendations from the joint ISPOR-ISPE Special Task Force on real-world evidence in health care decision making (<https://www.ncbi.nlm.nih.gov/pmc/articles/PMC5639372/>) and similar standards.

11. MANAGEMENT AND REPORTING OF ADVERSE EVENTS/ADVERSE REACTIONS

This study uses existing health care databases, in which it is generally not possible to link (ie, identify a potential association between) a particular product and medical event for any individual.

In addition, this study protocol requires human review of patient-level unstructured data; unstructured data refer to verbatim medical data, including text-based descriptions and visual depictions of medical information, such as medical records, images of physician notes, neurological scans, X-rays, or narrative fields in a database. The reviewers are obligated to report adverse events (AE) with explicit attribution to any Pfizer drug that appear in the reviewed information (defined per the patient population and study period specified in the protocol). Explicit attribution is not inferred by a temporal relationship between drug administration and an AE, but must be based on a definite statement of causality by a healthcare provider linking drug administration to the AE.

The requirements for reporting safety events on the non-interventional study (NIS) adverse event monitoring (AEM) Report Form to Pfizer Safety are as follows:

- All serious and non-serious AEs with explicit attribution to any Pfizer drug that appear in the reviewed information must be recorded on the chart abstraction form and reported, within 24 hours of awareness, to Pfizer safety using the NIS AEM Report Form.
- Scenarios involving drug exposure, including exposure during pregnancy, exposure during breast feeding, medication error, overdose, misuse, extravasation, lack of efficacy and occupational exposure associated with the use of a Pfizer product must be reported, within 24 hours of awareness, to Pfizer Safety using NIS AEM Report Form.

For these safety events with an explicit attribution to or associated with use of, respectively, a Pfizer product, the data captured in the medical record will constitute all clinical information known regarding these AEs. No follow-up on related AEs will be conducted.

All research staff members will complete the Pfizer requirements regarding training on the following: *“Your Reporting Responsibilities: Monitoring the Safety, Performance and Quality of Pfizer Products (Multiple Languages)”* and any relevant Your Reporting Responsibilities supplemental training. This training must be completed by research staff members prior to the start of data collection. All trainings include a “Confirmation of Training Certificate” (for signature by the trainee) as a record of completion of the training which must be kept in a retrievable format. Copies of all signed training certificates must be provided to Pfizer.

12. PLANS FOR DISSEMINATING AND COMMUNICATING STUDY RESULTS

In the event of any prohibition or restriction imposed (eg, clinical hold) by an applicable Competent Authority in any area of the world, or if the investigator is aware of any new information which might influence the evaluation of the benefits and risks of a Pfizer product, Pfizer should be informed immediately.

15. LIST OF FIGURES

None.

ANNEX 1. LIST OF STAND ALONE DOCUMENTS

None.

ANNEX 2. ENCEPP CHECKLIST FOR STUDY PROTOCOLS

Not applicable.

ANNEX 3. ADDITIONAL INFORMATION

Not applicable.

## 1 AMENDMENTS FROM PREVIOUS VERSION(S)

Amendment 1.0 expands the description of the statistical methods specified in the approved A5481122 Study Protocol (dated January 22, 2019) **CCI** methods related to the Exploratory objective: compare effectiveness of Palbociclib +

**CCI**

Amendment 2.0 describes an amendment to the Statistical Analysis Plan for Protocol A5481122, Amendment 1.0 (dated April 4, 2019). The changes to Amendment 1.0 can be identified by using the Track Changes option in Word.

Amendment 3.0 is prepared after the Flatiron Analysis Database transferred and locked. Primary and most secondary analysis had been already performed except detailed updates the analyses of treatment patterns in terms of initial dose, dose adjustment, time to treatment discontinuation, time to next line of therapy, and time to chemotherapy. It also examines the associations of initial Palbociclib dose (125mg, 100/75mg) with demographic and clinical characteristics, time to treatment discontinuation, real world PFS, real world tumour response, and OS if sample size is large enough for meaningful statistical analyses.

Text copied directly from Protocol A5481122 is italicized.

## 2 INTRODUCTION

*Palbociclib, the first oral CDK4/6 inhibitor, is approved for HR+/HER2– metastatic/advanced breast cancer (MBC) in combination with an aromatase inhibitor or fulvestrant. Improved median PFS was observed with Palbociclib plus Letrozole as first-line therapy (PALOMA-2) and with Fulvestrant in patients who have progressed on or after prior endocrine therapy in the adjuvant or metastatic setting (PALOMA-3). Since its approval in February 2015, Palbociclib has been prescribed for more than 100,000 patients. Recent real-world studies support the effectiveness of Palbociclib-based therapy in HR+/HER2– MBC patients. However data published to date have limitations including small cohorts, short duration of follow-up, inconsistent definitions of outcomes, and lack of a comparator. Electronic health record (EHR) data are collected as part of routine clinical practice and enable quick access to richer health information (as compared to claims database) in a timely manner (as compared to primary data collection) in a relatively large population. Utilizing Flatiron Health’s longitudinal, demographically and geographically diverse database derived from electronic health*

---

*record (EHR) data from over 265 cancer clinics (~800 sites of care), the current study is designed to describe patient characteristics, treatment patterns and effectiveness of Palbociclib in combination with an aromatase inhibitor (AI) as initial endocrine based therapy in HR+/HER2- MBC.*

## 2.1 STUDY DESIGN

**Study design:** *This is a retrospective cohort study utilizing data derived from the Flatiron Health Analytic Database to describe patient characteristics and effectiveness of Palbociclib + Letrozole and Letrozole alone as first line therapy in HR+/HER2- MBC during the period of February 3/2015 through 3 months prior to the data cutoff date of the current Flatiron data release in the US real-world clinical practice setting.*

- **Index date:** the start date of the first line therapy for Palbociclib + Letrozole or Letrozole alone between February 3, 2015 and 3 months prior to the cutoff date of the current data release. Index dates will be restricted to a date chosen to allow a potential duration of treatment of at least 3 months for all patients.
- **Observation period:** February 3, 2015 through the cutoff date of the current data release.
- **Follow-up:** Patients will be followed from the index date to the data cutoff date, or death, whichever came first.

**Data source:** *Flatiron Health's longitudinal, demographically and geographically diverse database is derived from electronic health record (EHR) data from over 265 cancer clinics (~800 sites of care) including more than 2 million active US cancer patients.* The analysis will use the following data sets:

Data Set Name	Description
Demographics	Contains patient demographic information. Data set consists of one record per patient.
Visit	Contains information on all visits including the visit date, type of information (vitals, treatment, and/or lab) collected during the visit. Data set consists of one record per patient per visit.
ECOG	Contains information about ECOG performance status including the ECOG date and value. Data set consists of one record per patient per ECOG record.

LineOfTherapy	Contains information about each line of therapy received by the patient, as defined by Flatiron business rules including the line number, line name, start and stop dates for the line. Data set consists of one record per patient per line of therapy.
Enhanced_Mortality_V2	Contains the month and year in which the patient died. The complete date is not provided due to patient confidentiality reasons. Data set consists of one record per patient for patients who died.
Enhanced_MetastaticBreast	Contains the initial diagnosis date and initial MBC date and the Stage at the initial diagnosis. Data set consists of one record per patient.
Enhanced_MetBreastSitesOfMet	Contains information on the sites of metastasis at the time of MBC diagnosis. Data set consists of one record per patient.
Enhanced_MetBreastProgression	Contains the date of the last clinic visit note in the patient's chart, progression event dates, and information on the source of evidence for progression reported by the treating physician. Data set consists of one record per patient without progression. For patients with progression the data set consists of one record per progression event date.

**Treatment/cohort labels:** After applying the inclusion and exclusion criteria, eligible patients will be assigned to the following cohorts based on their first line MBC treatment.

- ***Palbociclib + Letrozole Cohort:*** patients who initiated Palbociclib plus Letrozole therapy as their first line MBC treatment
- ***Letrozole alone Cohort:*** patients who initiated Letrozole therapy as their first line MBC treatment

## 2.2 STUDY OBJECTIVES

The following objective of the study protocol will be addressed by the analysis described in this amendment to the SAP:

CCI

### 3 HYPOTHESES AND DECISION RULES

CCI [REDACTED]

[REDACTED]

CCI [REDACTED]

[REDACTED]

#### 3.2 STATISTICAL DECISION RULES

The alpha level for statistical significance will be set at a two-tailed level equal to 0.05.

#### 3.3 SAMPLE SIZE CALCULATION

All eligible patients meeting study inclusion/exclusion criteria will be included in the analysis. A preliminary count of first-line Letrozole alone and Palbociclib + Letrozole patients indicated each cohort will contain over 650 patients. Based on the PALOMA-2 clinical trial, the median PFS of the Letrozole alone group was equal to 14.5 months compared to 24.8 months for the Palbociclib + Letrozole group. Assuming similar median rwPFS survival rates and using yearly accrual rates from the Flatiron data extract, a survival analysis of rwPFS would require 138 patients in each group. The sample size calculation used the assumptions of a two-tailed alpha of 0.05, power of 90%, an accrual period (i.e., the time period when patients are identified until study end [03FEB2015-31AUG2018]) of 3.6 years. Robust variance estimation will be used to compute the adjusted proportional HR in the IPTW analysis; therefore, the sample size presented here may be overestimated.

### 4 ANALYSIS SETS/ POPULATIONS

#### 4.1 FULL ANALYSIS SET

##### Inclusion criteria

*Patients must meet all of the following inclusion criteria to be eligible for inclusion in the study:*

1. *Female sex*
2. *At least 18 years old at MBC diagnosis*
3. *Diagnosis of MBC at any point in patient history*
  - a. *ICD-9 (174.x, 175.x) or ICD-10 (C50.xx) diagnosis of BC*
  - b. *Confirmation of metastatic disease*

- c. *At least 2 document clinical visits*
  - d. *Evidence of stage IV or recurrent MBC with a metastatic diagnosis date on or after 2011, as confirmed by unstructured clinical documents*
4. *HR+/HER2-*
  - a. *HR+: ER+ or PR+ test before or up to 60 days after MBC diagnosis*
  - b. *HER2-: any HER2 negative test and the absence of a positive test (IHC positive 3+, FISH positive/amplified, Positive NOS) before or up to 60 days after MBC diagnosis*
5. *Palbociclib + Letrozole or Letrozole alone as first line therapy for MBC during the period from February/2015 through three months prior to data cutoff to allow for a possible minimum follow-up time of 90 days until the data cutoff date. Letrozole in the Palbociclib + Letrozole cohort was administered within ( $\pm$ ) 28 days of Palbociclib index date.*

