9. RESEARCH METHODS

9.1. Study Design

A retrospective cohort study of treatment patterns and effectiveness of Palbociclib + AI as initial endocrine based therapy during the period February/3/2015 through August/31/2018 (or 3 months prior to study cut-off date) for MBC will be conducted utilizing secondary de-identified Flatiron Healthcare Analytic data in the United States. This study design is selected to meet the study objectives with consideration of feasibility and availability and validity of exiting database.

- **Index date:** the date of first prescription for + AI between February 3, 2015 and August 31, 2018 (or 3 months prior to study cut-off date).
- **Observation period:** February 3, 2015 – study cut-off date.
- **Follow-up:** Patients will be followed from the index date to the end of the study (study cut-off date) or death, whichever came first.
 - **Primary endpoints**
 - RwPFS.
 - **Secondary endpoints**
 - OS.
 - RwTR.
 - Response rate.
 - Real-world duration of treatment (rwDOT).
 - Time from index date to next line of anti-cancer therapy and time to first use of chemotherapy.

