Time to treatment discontinuation	
 
The time from the start of a treatment to the time of treatment discontinuation for any reason in 1LOT
 
Start date: PAL/AI start date in 1LOT
 
End date: 
 
A. PAL/AI end date in 1LOT
 
B. 2LOT start date
 
C. Death date in 1LOT
 
D. Whichever came first
 
 
 
Censoring date: latest available drug administration or latest visit/activity date (lab, office, radiology, etc), end of study, or loss to follow-up, whichever came first.
 
2LOT start date 
 
A. Start date of adding any new anti-neoplastic (chemotherapy, target therapy (eg., Abemaciclib, Ribociclib), or endocrine therapy) if there is evidence of disease progression or after 60 days of index date if there is no evidence of disease progression.
 
B. AI discontinuation or exchange from one AI to another AI is not considered as 2LOT start if there is no evidence of disease progression
 
C. Exchange from one PAL to another CDK4/6i AI is not considered as 2LOT start if there is no evidence of disease progression.
 
D. 1LOT was not advanced if PAL and/or AI were paused or stopped and then restarted within 120. Different days (90, 120, and 180) will be used as sensitivity analyses.
 
 
 

Organ-level metastatic sites	Number of sites; Sites of metastases (bone, lung, liver, brain, distant lymph nodes, other) Visceral vs. non-visceral, bone only
Modified Charlson comorbidity index (CCI)	As defined in the Flatiron database
Effectiveness outcomes	
Overall survival (OS)	
Time in months from index date to death due to any cause or censoring date will be calculated.
 
Based on an improved understanding of the death information in Flatiron and a better understanding of the OS analysis in PALOMA-2 the following changes will be made to the OS outcome definition.
 
Event: Any death recorded by Flatiron in the data extract. Patients who did not die will be censored at the time of data cutoff.

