Real-world PFS (rwPFS)	
Time in months from index date to progression or censoring date will be calculated.
 
Based on improved understanding of the PFS analysis in PALOMA-2 the following changes will be made to the PFS outcome definition.
 
Event: Any death or disease progression (concluded by the treating clinician based on radiology, laboratory evidence, pathology, or clinical assessment). If patients did not die or have disease progression, they were censored at the date of initiation of next line of therapy for patients with two or more lines of therapy or their last visit date during the study period for patients with only one line of therapy.

Real-world tumor responses (rwTR)	
 
● Complete response: complete resolution of all visible disease.
 
● Partial response: partial reduction in size of visible disease in some or all areas without any areas of increase in visible disease.
 
● Stable disease: no change in overall size of visible disease; also included cases where some lesions increased in size and some lesions decreased in size
 
● Progressive disease: an increase in visible disease and/or presence of any new lesions; included cases where the clinician indicated progressive disease.
 

Response rate	
 
● Complete response or partial response divided by the number of patients with at least one tumor assessment while on the index treatment.
 

Time to next line of anti-cancer therapy	
 
● Defined as the time from the initiation of 1LOT (PAL+AI) until either 
 
○ the day before the start of 2LOT for patients with evidence of 2LOT, or
 
○ death if the death occurred within 60 days following the patient's last administration of 1LOT (PalB/AI)
 
○ Whichever occurred first.
 
 
 
● If a patient did not have evidence of 2LOT and did not die within the 60 days following the last 1LOT administration, the patient was censored at the latest available date that occurred on or before the end of study date of either last drug administration plus the number of days in a treatment cycle (last PAL/AI administration + 28 days) last visit date (e.g., office visit, lab, radiology, etc), or data cutoff date.
 

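### The rwPFS and OS clocks start at first-line start, but combination membership can depend on a second drug begun up to 28 days later; the SAP neither corrects for this nor settles where day 29-60 palbociclib additions belong

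*SAP*

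**What the plan says.** **Time zero.** SAP 2.1 sets the index date for both cohorts as "the start date of the first line therapy for Palbociclib + Letrozole or Letrozole alone". Line dates come from the data vendor's business rules, and the SAP does not say which drug sets the line start. Protocol 9.1 instead uses a prescription date: "the date of first prescription for + AI between February 3, 2015" (the drug name before the plus sign is missing in the text available).

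**Clock.** SAP 2.1 states: "Patients will be followed from the index date to the data cutoff date, or death, whichever came first". For rwPFS, SAP 5.1 states: "Time in months from index date to progression or censoring date will be calculated". OS also runs from index.

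**Membership.** SAP 4.1, inclusion criterion 5, sets the timing rule: "Letrozole in the Palbociclib + Letrozole cohort was administered within" plus or minus "28 days of Palbociclib index date". This is a third way of naming the anchor. The same criterion admits the comparator as letrozole alone, whereas the cohort label in SAP 2.1 defines it by letrozole having been initiated.

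**Later additions.** Within the definition of time to treatment discontinuation, SAP 5.1 starts a second line when a new agent is added after progression, or "after 60 days of index date if there is no evidence of disease progression".

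**Adjustment.** SAP 6 plans IPTW and propensity-score matching on baseline covariates. The readable text has no landmark, time-varying exposure or grace-period method.

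**The concern.** Take a patient who starts letrozole on day 0 and is due to add palbociclib on day 20. If she progresses or dies on day 10, she never receives palbociclib and is counted under letrozole alone. If she reaches day 20 without an event, she is counted as combination from day 0. Her 20 days are immortal time in the combination cohort, and her counterpart's event goes to the comparator. If palbociclib came first, a patient with an event before letrozole starts fits neither cohort label and drops out. That also removes an early event from the combination side.

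Both routes lower the hazard ratio. rwPFS is the primary outcome of the palbociclib + letrozole versus letrozole comparison in SAP 6, and OS is a secondary one. Propensity methods balance what is known at baseline. They do not repair a classification made after it.

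The same issue arises after day 28. If patients who add palbociclib on days 29-60 are excluded, that exclusion also conditions on treatment after index.

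**Working it through.** **Inputs.** Median PFS 14.5 and 24.8 months, and an identification period of 3.6 years = 43.2 months (SAP 3.3); 3 months between last index date and cutoff (SAP 2.1); a 28-day window (SAP 4.1); 1,221 palbociclib + letrozole and 627 letrozole patients (Protocol 9.5). Assumed, because the documents do not give them: exponential event times, gaps uniform on 0-28 days, and the share f of combination patients with staggered starts.

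**The plan's own figure.** The bias does not depend on the sample size, but reproducing it supports the censoring pattern. The planning hazard ratio is 14.5/24.8 = 0.585. Freedman's formula (two-sided 0.05, 90% power) gives 153 events. With uniform accrual over 43.2 months plus 3 months, the event probabilities are 0.634 and 0.466, mean 0.550. Then 153/0.550 ≈ 278, or about 140 per group, against the stated 138. I therefore use administrative censoring between 3 and 46.2 months.

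**Risk inside the window.** Letrozole hazard λ = ln 2/14.5 = 0.0478 per month. The window is G = 28/30.44 = 0.920 months, so λG = 0.0440.
- Event within 28 days: 1 − exp(−0.0440) = 4.3% (2.5% at a 24.8-month median).
- Event before the second drug, averaged over uniform gaps: 1 − 0.0430/0.0440 = 2.17%.

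**Null case, all staggered starts letrozole-first.** Expected events without misclassification are 1,221 × 0.634 = 774.1 and 627 × 0.634 = 397.5. Person-time per patient is 0.634/0.0478 = 13.26 months, giving about 16,190 and 8,314 months. The person-time that moves is negligible (at most 26.5 patients × 0.92 months). The number reclassified is 1,221 × f × 0.0217.

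| f | Reclassified | Combination events | Letrozole events | Rate ratio |
|---|---|---|---|---|
| 10% | 2.6 | 771.5 | 400.1 | 0.99 |
| 30% | 7.9 | 766.2 | 405.4 | 0.97 |
| 50% | 13.2 | 760.9 | 410.7 | 0.95 |
| 100% | 26.5 | 747.6 | 424.0 | 0.91 |

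An unweighted Cox simulation with the same inputs gives the same four values.

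**Variations under the null.**
- Half the staggered starts palbociclib-first (their early events dropped): about 0.97 at 50% and 0.94 at 100%.
- No administrative censoring, all letrozole-first: 0.94 at 100%.
- Equal cohort sizes, all letrozole-first: 0.966 at 50% and 0.936 at 100%.
- Clock started at the second drug, equal cohort sizes: 0.992, 0.983 and 0.968 at 25%, 50% and 100%. Moving the anchor alone does not remove the bias.

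**True hazard ratio 0.585, all letrozole-first.** At equal cohort sizes the estimate is about 0.577 at 25% and 0.568 at 50%. A repeat at 1,221:627 gives about 0.57 and 0.56.

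**Day-28 landmark.** The simulated hazard ratio returns to 1.00 under the null and to 0.584-0.586 when the truth is 0.585. The share retained at equal cohort sizes is 1 − (0.043 + 0.025)/2 = 96.6%. The 138 per group would become 138/0.966 ≈ 143, against the more than 650 per cohort stated in SAP 3.3.

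**Additions on days 29-60 without progression.** The SAP 2.1 label (letrozole initiated) keeps them in the letrozole cohort. Criterion 5 (letrozole alone), read with the 60-day rule, leaves the addition in first line, so the patient meets neither the 28-day rule nor the letrozole-alone condition. The two readings give different cohorts.

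**The case against.** The strongest reply is that the effect is small and partly a matter of reading. Much of that stands.

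- **Size.** No more than 28 days per patient are affected and same-day starters contribute nothing. At 25% staggered and equal cohort sizes, 0.585 becomes about 0.577. The larger null figures need most starts to be staggered and all of them letrozole-first.
- **Anchor.** That the clock starts at the first drug is the natural reading of a line start, but it is not written, and criterion 5 names a palbociclib index date. The bias is smaller, though still present, if the clock starts at the second drug.
- **Early events.** A reader might infer that early events can fall only on the letrozole side. The documents do not support this: same-day starters, and staggered starters after their second drug, can have early events in the combination cohort, and a palbociclib-first patient with an early event drops out.
- **Neither cohort.** A reader might infer that day 29-60 additions are in neither cohort. That borrows a rule from the time-to-discontinuation definition, which is written for palbociclib + AI, applies only without progression, and conflicts with the SAP 2.1 label. What stands is that the SAP does not settle the matter.
- **Redaction.** Blacked-out text may hold further assignment rules.

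None of this supplies a correction. Baseline weighting and matching leave the post-index classification in place.

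**Conclusion.** The point holds as a modest, one-directional bias plus an undefined assignment rule. As readable, the plan classifies on information up to 28 days after time zero and analyses rwPFS and OS from time zero, which favours the combination. Under the null the plausible range runs from about 0.99 (10% staggered) to 0.91 (all staggered and letrozole-first), and to 0.94 if half of those are palbociclib-first. These values rest on exponential times, uniform gaps and an assumed staggered share. They size rwPFS only; the documents give no survival figure from which to size OS. This does not explain away a difference as large as the planning hazard ratio, but it is avoidable and cheap to check.

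**What to change.** 1. Reconcile Protocol 9.1 with SAP 2.1 (index date and cohort labels), 4.1 and 5.1 to one time zero: the start of the first first-line drug.
2. Report the distribution of the gap between the two drug starts, and which drug came first.
3. Add a day-28 landmark sensitivity analysis for rwPFS and OS. Classify patients by the drugs started by day 28, start follow-up at day 28 in both cohorts, and keep later palbociclib additions in the letrozole-alone cohort.
4. State how day 29-60 additions are analysed, for example left as assigned, with a second run censoring at the addition. The existing next-line rule does not reach these patients when there is no progression.
5. For OS, give a rule for deaths near day 28, because the mortality file described in SAP 2.1 holds only month and year of death.

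The cost is SAP wording and a re-run. About 3-4% of patients are left out through an event before day 28, plus any whose follow-up ends before then. SAP 1 says Amendment 3.0 followed database lock with the primary and most secondary analyses done, so this analysis should be labelled post hoc.
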